STUDY PROTOCOL SYNOPSIS

Promoter: University Milano-Bicocca

Product: Imatinib

Title of Study: Validation of digital-PCR analysis through programmed imatinib interruption in PCR negative chronic myeloid leukemia patients.

Protocol Acronym: ISAV

Background Information and Study Rationale:

Chronic Myeloid Leukemia

Chronic myeloid leukemia (CML) represents 7–20% of all leukemia cases, with a worldwide incidence projected at one to two per 100,000 people (1). CML is caused by the unregulated activity of the tyrosine kinase BCR/ABL (2), which is formed by the fusion of exons belonging to the BCR and ABL genes, located on chromosomes 22 and 9 respectively (3), that generates the Philadelphia (Ph) chromosome (4).

Untreated CML commonly progresses through three disease phases: chronic phase (CP), accelerated phase (AP) and blast phase (BP), each corresponding to increasing leukemic blast counts and clinical severity. The chronic phase (CP), that usually lasted 2-3 years in the pre-imatinib era (5), is characterized by an abnormal expansion of the clonal hematopoiesis retaining an apparent normal differentiation; the AP's median duration is 3-9 months, while BP's median survival is 3-6 months (6). The last two phases are marked by the development of a differentiation block typical of acute leukemia which fatally closes the course of the disease (7).

Imatinib Therapy

The main goal of CML therapy is the suppression of Ph+ clone in the chronic phase (CP) (8). Since BCR/ABL translocation represents the molecular cause of CML, the targeting of its enzymatic activity represents a truly “targeted” attempt to cancer therapy. In fact, over the last two decades, the therapy evolved from the use of non-specific cytotoxic agents (i.e. hydroxurea, busulfan) (9, 10) to interferon- α (IFN- α) (11-15) or allogeneic stem cell transplantation (allo-SCT) (16-22) and more recently to imatinib, a competitive inhibitor of the BCR/ABL kinase that, with a 5-year survival rate greater than 90%, is now recognized as the first-line treatment of CML (16-26) and could allow a normal life expectancy (27).

Imatinib induces complete cytological response (CCyR) in up to 80% of patients (33) and major molecular response (MMR) in 33-90% of the patients, according to treatment duration. Moreover, approximately 1/3 of long term treated patients who are in CCyR show complete molecular response (CMR, i.e. undetectable BCR/ABL transcripts) and absence of residual sign of leukemia (27). Anyway, undetectable BCR/ABL may not equate to eradication of minimal residual disease (MRD) because the sensitivity of the standard diagnostic method, the Q-RT-PCR, is limited and significant numbers of residual leukemic cells can remain in a patient (33).

The digital-PCR assay

The development of a more sensitive Q-RT-PCR to monitor MRD was recently included among the study endpoints of the ILTE study, aimed to present a global picture of imatinib long term effects (serious adverse events (SAE), toxicities not qualifying as SAE, loss of CCyR, survival). A pilot study was performed on blood samples obtained from patients who remained negative for at least

Promoter: University Milano-Bicocca

Product: Imatinib

one year, using a new diagnostic method, the digital-PCR (dPCR), developed by [name], [name] and [name] (39), able to detect until 1 BCR/ABL+ cell out of 10^7 cells, which corresponds to a 100 times increased sensitivity as compared to conventional Q-RT-PCR (45). The results showed that, among 30 patients negative by conventional Q-RT-PCR for at least one year, only 10 patients (33%) were negative by dPCR. Interestingly, these numbers are compatible with those observed in a French study in which about 40% of patients were relapse-free within 12 months from imatinib suspension (27). Therefore, it is possible that dPCR, assessing with more sensitivity the presence of MRD, could better identify the patients where CML is truly eradicated.

Study Rationale

Imatinib treatment for CML is recommended to be life long, but pilot studies showed that it is possible to suspend imatinib treatment without experiencing relapse (32). According to several models predicting CML cell proliferation based on the cell doubling time, at least 6 months are necessary to reach a number of cells detectable by Q-RT-PCR if a single CML cell persists in the patient when imatinib is suspended. Therefore, after 6-8 months of imatinib suspension without relapse, it is possible to hypothesize that the disease is eradicated or that residual CML cells are in a quiescent state (38). In this condition, it is estimated that imatinib discontinuation might be permanent (36, 37, 40), allowing to achieve two important advantages:

- a substantial reduction in health care spending (about 3 millions euro/year saved every 100 such patients by the NHS)
- the prevention of the morbidity due to imatinib side effects.

Nowadays, it remains possible that during the interruption period the disease could progress in the majority of patients because it is not possible to surely identify “a priori” patients with CMR able to permanently discontinue imatinib. In fact no diagnostic assay is sensitive and specific enough to predict the disease relapse after the therapy discontinuation. Therefore, it is only possible to rely on a “watching and wait” strategy. Importantly, the relapse is reversible upon imatinib resumption (35, 36).

The present study is aimed to evaluate if the new dPCR method, able to detect a single BCR/ABL positive cell out of 10^7 cells (compared to 1 cell out of 10^4 - 10^5 for standard Q-RT-PCR), could predict CML reappearance after imatinib discontinuation in the setting of Q-RT-PCR negative CML patients.

In case of positive results, a rational drug suspension policy which relies on dPCR status for the decision of stopping or continuing imatinib treatment will be allowed.

Objectives:

Primary Objective

Evaluation of the power of the dPCR technique to predict disease relapses after imatinib discontinuation in CML patients with negative Q-RT-PCR results since more than 18 months.

Secondary Objectives

- Evaluation of dPCR technique specificity.
- Evaluation of the maintenance of molecular remission, after imatinib discontinuation, in CML patients with negative Q-RT-PCR results since more than 18 months.

Promoter: University Milano-Bicocca

Product: Imatinib

- Evaluation of quality of life in CML patients after imatinib discontinuation/resumption.
- Evaluation of progression/resistance in patients who relapse after imatinib discontinuation.

Endpoints:

Primary Endpoint:

- Negative Predicted Rate (NPV) of dPCR, i.e. the capability of the method to predict relapse-free patients.

Secondary Endpoints:

- Rate of dPCR positive relapse-free patients after 3 years follow up.
- Rate of relapse-free patients after 3 years follow up.
- Relapse free time.
- Quality of Life, as measured by EORTC-QLQ-T30 questionnaire.
- Rate of patients progressing or developing resistance after imatinib suspension.

Study Design and Methods:

In this study dPCR analysis will be performed on CML patients under imatinib therapy, with at least 18 months of consecutive negative standard Q-RT-PCR as performed in their own centers. The patients will sign an informed consent form (ICF), will subsequently be tested for dPCR and will stop imatinib. Then they will be monitored with standard Q-RT-PCR to assess the maintenance of the molecular remission. Collection of data will be prospective as each center will collect the data for 36 months. At the end of this period, a peripheral blood sample for dPCR analysis will be obtained from those patients who will still have undetectable BCR/ABL transcripts by Q-RT-PCR to verify CML eradication. Two years follow-up is then planned for patients maintaining CMR. During study, the patients with BCR/ABL transcripts detected by standard Q-RT-PCR will repeat the test not before 2 weeks and not after 2 months; in case of results confirmation and at least one BCR/ABL / BCR value >0.1%, the loss of the molecular remission will be declared and hematologic and bone marrow analyses will be performed. Such patients will immediately resume imatinib treatment at the same dosage used before interruption; progression of the disease will be evaluated as evolution to AP or BP and resistance to treatment will be defined as lack of complete hematological response at 3 months or of complete cytogenetic response at 6 months after resuming imatinib.

Patient's life quality during imatinib discontinuation/resumption will be evaluated through a Quality of Life (QoL) questionnaire until the end of this study (for patients maintaining molecular remission at baseline and at months 1, 6, 12, 24, 36, for relapsing patient at months 1, 6, 12 after imatinib resumption).

The eligible patients will be entered between September 2011 and August 2012. Approximately 14 Centers will be involved in the study, including 5 international Centers.

Sample size

Sample size will be calculated so to provide with 80% power the alternative hypothesis that the Negative Predicted Value (NPV) of dPCR (i.e. the capability of the method to predict relapse-free patients) will exceed the one of traditional Q-RT-PCR, by more than 1.5.

$$H_0(N): rNPV \leq \delta$$

$$H_1(N): rNPV > \delta$$

where rNPV is the ratio of the Predicted Negative Values by the two tests respectively.

Promoter: University Milano-Bicocca

Product: Imatinib

With reference to the table below:

$$rNPV = \frac{NPV_{dPCR}}{NPV_{Q-RT-PCR}} = \frac{(n_{3+} n_4) / (n_{3+} n_4 + n_{6+} n_8)}{(n_{2+} n_4) / (n_{2+} n_4 + n_{6+} n_8)}$$

	Relapse Free 3 years since discontinuation			Relapsed within 3 years since discontinuation		
	Q-RT-PCR at entry			Q-RT-PCR at entry		
dPCR at entry	Positive	Negative	Total	Positive	Negative	Total
Positive	n ₁	n ₂	n ₁₊ n ₂	n ₅	n ₆	n ₅₊ n ₆
Negative	n ₃	n ₄	n ₃₊ n ₄	n ₇	n ₈	n ₇₊ n ₈
	n ₁₊ n ₃	n ₂₊ n ₄	N _{R-}	n ₅₊ n ₇	n ₆₊ n ₈	N _{R+}

The studies estimating the relapse rate of patients after discontinuation of imatinib are still limited in number, based on a relatively low number of patients, heterogeneous by time on treatment, observation time accrued after discontinuation and therapy preceding imatinib (39, 40, 41). According to the preliminary results of the STIM study (40) that included patients in CMR for at least 24 months, 42 out of 69 patients followed for 13-30 months (median 24 months) since imatinib discontinuation relapsed. Thirty-nine percent (95% CI 28-51%) of patients were still negative at Q-RT-PCR performed at repeated occasions after discontinuation. Due to the lack of robust estimates, the sample size has been calculated assuming that $NPV_{Q-RT-PCR}$ equals to the lower limit of the 95% CI of the relapse free rate reported above i.e. 28%. If true rate of $NPV_{Q-RT-PCR}$ is higher the sample will provide the test with more power. Also, according to a pilot experience conducted within ILTE protocol, only 1/3 of patients negative by Q-RT-PCR are also negative by dPCR. Finally, n₃ and n₇ were assumed to be 0 because, being the dPCR method more sensitive than Q-RT-PCR, it is highly unlikely that the former turns to be negative when actually the latter is positive. With $\alpha=0.05$, $\beta=0.20$, $\delta=\gamma=1.5$ under the alternative hypothesis and the above assumptions the sample size required calculated according to reference (42) is 98 patients.

Definition of Analyzed Study Populations

All enrolled patients will be evaluated. Patients who withdraw or die before 36 months from the day 1 of the study will be considered as not evaluable.

Analyses

The data will be analyzed by Milano International Oncology or designee. rNPV will be calculated as the ratio of the Predicted Negative Values by the two tests respectively. If the lower 95% confidence limit will be greater than 1.5 one would conclude that the new method is more effective in predicting negative value as compared to the traditional one.

Progression free survival computed as the day since enrolment to the day of relapse or death will be analyzed by Kaplan-Maier method. The sensitivity and specificity of dPCR to predict molecular relapse will be assessed, as well as the overall and progression free survival of patients.

Promoter: University Milano-Bicocca

Product: Imatinib

The following variables will be monitored: dPCR results, number and time of relapses (molecular, cytogenetic or hematological), presence of progression AP/BP at relapse, best response obtained after imatinib reintroduction. Quality of life will be evaluated before and after imatinib suspension and after eventual imatinib resumption.

Interim Analyses:

Interim analyses will be conducted 1, 2 and 3 years after the day of last patient enrollment.

Subject Selection:

Subject inclusion criteria:

Subjects must meet all of the following inclusion criteria to be eligible for enrollment into the study:

1. Signed and dated IRB/IEC-approved Informed Consent.
2. Age > 18 years.
3. Male or female patients with CML diagnosed in chronic phase and who have been treated for more than 2 consecutive years with Imatinib therapy.
4. Achievement of CMR (as defined by their own center) sustained for at least 18 months with imatinib treatment.
5. A minimum of 3 CMR determined by Q-RT-PCR analysis to support disease status, with the last one performed within 3 calendar months prior to enrollment date.
6. Willingness and ability to comply with scheduled visits, laboratory tests and other study procedures.

Subject Exclusion Criteria:

The presence of any of the following will exclude a subject from study enrollment:

1. Allogenic hematopoietic stem cell transplantation.
2. Known active infections, including human immunodeficiency virus (HIV) positivity.
3. Current enrollment in another clinical trial.
4. Other severe acute or chronic medical or psychiatric condition or laboratory abnormality that may increase the risk associated with study participation or study drug administration or may interfere with the interpretation of study results and, in the judgment of the Investigator, would make the patient inappropriate for entry into this study.

Trial Product

In case of loss of molecular remission the patients will resume imatinib treatment at the same dosage used before interruption. In case of treatment resumption, imatinib will be administered as home-based treatment. Imatinib is marketed and used for the treatment of CML so it do not represent an additional cost for the study and will be supplied by the National Health Service. Imatinib is commercially available in rigid capsules of 50 mg. Imatinib is to be stored at room temperature not exceeding + 30°C and in the original packaging, out of the reach and sight of children.

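### Wrong as written: a fixed 1.5 margin on a ratio whose denominator contains its numerator makes the primary success rule turn on the dPCR-negative share as well as on how well dPCR predicts relapse

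*Protocol*

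**What the plan says.** The primary objective is "Evaluation of the power of the dPCR technique to predict disease relapses" after imatinib is stopped in Q-RT-PCR-negative patients. The primary endpoint is the NPV of dPCR.

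Under Sample size, the alternative is that this NPV "will exceed the one of traditional Q-RT-PCR, by more than 1.5". The test quantity is rNPV, "where rNPV is the ratio of the Predicted Negative Values by the two tests respectively". The calculation is introduced by "With $\alpha=0.05$, $\beta=0.20$, $\delta=\gamma=1.5$ under the alternative hypothesis" and gives 98 patients. It takes the NPV of Q-RT-PCR as 28%, and from the pilot it takes it that "only 1/3 of patients negative by Q-RT-PCR are also negative by dPCR". Cells n3 and n7 are assumed to be zero because dPCR is the more sensitive test.

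Under Analyses, the new method is judged more effective "If the lower 95% confidence limit will be greater than 1.5".

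Under Study Design and Methods and in the inclusion criteria, all patients have at least 18 months of negative Q-RT-PCR, supported by "A minimum of 3 CMR determined by Q-RT-PCR analysis to support disease status".

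**The concern.** The two NPVs come from one group and from a cohort that contains it. Q-RT-PCR does not vary at entry in this trial, so its NPV is simply the overall relapse-free rate. The protocol treats it that way itself, setting it to the lower confidence limit of a cohort relapse-free rate from an earlier discontinuation study. The more patients are dPCR-negative, the more the denominator is made up of the numerator group, and the closer the ratio is pulled to 1.

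With a margin of 1.5 on such a ratio, the same separation between dPCR-negatives and dPCR-positives can pass or fail according to how many patients happen to be dPCR-negative. That is not what the primary objective asks. The protocol says positive results would support stopping or continuing imatinib according to dPCR status, so the rule that defines a positive result matters. It makes no allowance for a share other than 1/3, and that figure rests on 10 negatives "among 30 patients negative by conventional Q-RT-PCR for at least one year".

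**Working it through.** **Notation.** p = dPCR-negative share; A = 3-year relapse-free rate in dPCR-negatives (the NPV); C = that rate in dPCR-positives (1-PPV); RR = A/C; B = whole-cohort rate = pA + (1-p)C. I take the NPV of dPCR from the dPCR-negative row of the table, n4/(n4+n8). The printed formula has n6 where that row has n7. This is a separate error; taken literally with n3 = 0, the printed ratio cannot exceed 1.

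**Step 1: the plan's own figure.** Inputs from Sample size: p = 1/3, B = 0.28, rNPV = 1.5. Hence A = 0.28 × 1.5 = 0.42 and C = (0.28 - 0.42/3)/(2/3) = 0.21, so RR = 2.

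With p4 = pA = 0.14, the delta-method variance of ln rNPV is V/N, where

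V = 1/p4 - 1/p - 1/B + 2·p4/(pB) - 1 = 7.143 - 3 - 3.571 + 3 - 1 = 2.571.

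N = (z_α + z_β)² V / (ln(γ/δ))²:

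- Null ratio 1, one-sided 5%: (1.645 + 0.842)² × 2.571 / (ln 1.5)² = 96.7, so 97. This reproduces the stated 98 to within one patient.
- Null ratio 1, two-sided 5%: 123. This does not reproduce it.
- δ = γ = 1.5 as printed: ln(γ/δ) = 0, and no finite N exists.

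So the 98 rests on a null of 1, while the success rule uses 1.5.

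**Step 2: what 1.5 demands.** rNPV = A/(pA + (1-p)C) = 1/(p + (1-p)/RR) ≤ 1/p. Setting rNPV > 1.5 gives RR > (1-p)/(2/3 - p).

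| p | largest possible rNPV | RR that rNPV must exceed 1.5 with |
|---|---|---|
| 0.20 | 5.0 | 1.7 |
| 1/3 | 3.0 | 2.0 |
| 0.50 | 2.0 | 3.0 |
| 0.53 | 1.9 | 3.4 |
| 0.60 | 1.67 | 6.0 |
| 2/3 | 1.5 | none |

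The exact 95% interval for 10/30 is 0.17 to 0.53. Within it the required RR runs from about 1.7 to 3.4.

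**Step 3: chance of meeting the rule.** Simulation with N = 98, 200,000 trials per setting, a binomial number of dPCR-negatives, and the lower limit ln rNPV - z·√(V/N) compared with ln 1.5. The protocol does not state whether the limit is one- or two-sided; the one-sided 95% limit is used unless noted.

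| A versus C | p | rule met |
|---|---|---|
| 80% v 20% | 1/3 | 85% |
| 80% v 20% | 0.45 | 37% |
| 80% v 20% | 0.50 | 16% |
| 80% v 20% | 0.53 | 8% |
| 42% v 21% (planning values) | 1/3 | 6% |

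With a two-sided 95% limit, the 80%/20% test passes about 75% at p = 1/3, 8% at 0.50 and 3% at 0.53; the planning values pass about 3%.

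**Step 4: the same data against a null of 1.** rNPV > 1 means A > pA + (1-p)C, which is A > C whatever p is. For the 80%/20% test at each p above, rNPV tested against 1 succeeds in about 100% of trials, and so does a score test of the two dPCR groups. With no true difference, the size at nominal one-sided 5% is about 7.5% for the log-scale Wald limit on rNPV and 5.4% for the score test.

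**The case against.** The strongest reply is that the nested ratio is not itself the fault. Step 4 shows that with a null of 1 it gives the same hypothesis as a direct comparison, and the listed failures vanish. That stands, and it locates the cause: a 1.5 margin applied to a nested ratio. Nor is rNPV meaningless. It measures the gain over letting every Q-RT-PCR-negative patient stop, and that gain does shrink as p rises. Replacing it as the primary measure is therefore partly a matter of preference.

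It can also be said that the conflict between the null of 1 behind the 98 and the 1.5 in the rule is the more basic defect, since it causes failure at the planned share already. This too stands, and both are cured together.

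Four stronger readings are tempting, and the documents do not support them:

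- **A perfect test is bound to fail.** The rule is unattainable only at p ≥ 2/3, which lies well outside the pilot's interval. At p = 1/3 the ceiling is 3.0 and does not bind, and a perfect predictor still passes about 82% of the time at p = 0.53.
- **The share will be higher here because 18 months of negativity is required rather than one year.** This is possible, but the documents give no share at 18 months.
- **A failed trial would say nothing about prediction.** The NPV of dPCR, the rate of dPCR-positive relapse-free patients, sensitivity and specificity are all planned, and the direct contrast can be computed from them.
- **The threshold itself moves with p.** It does not. It is fixed at 1.5; what moves is the contrast between dPCR groups that it represents.

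**Conclusion.** The success rule is wrong as written. Across dPCR-negative shares that the protocol's own pilot allows, a strong predictor (80% versus 20%) goes from about 85% to about 8% chance of success with no change in its predictive strength. At the planning values the chance is about 6% (3% with a two-sided limit) where 80% is stated.

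This rests on eligibility making every patient Q-RT-PCR negative, on 98 evaluable patients, on reading the NPV of dPCR from the table, and on a delta-method limit on the log scale. The 80%/20% pair is illustrative; at p = 1/3 it implies a cohort rate of 40%, close to the 39% the protocol cites. The algebra in Step 2 needs none of the simulation assumptions.

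**What to change.** 1. Remove the requirement that the lower 95% limit exceed 1.5, and reconcile the hypotheses, δ = γ = 1.5 and the 98 patients, which correspond to a null of 1 at one-sided 5%.
2. Base the primary decision on the null of no difference in 3-year relapse-free rate between dPCR-negatives and dPCR-positives (equivalently rNPV > 1), using a score test with its sidedness stated.
3. Report NPV, 1-PPV and their ratio or difference with score intervals. Keep rNPV, if wanted, as a descriptive measure of gain over Q-RT-PCR alone.
4. State that n1, n3, n5 and n7 are zero by eligibility.

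**Cost.** Mainly wording; the data are already to be collected. The claim becomes weaker than a 1.5-fold gain. The honest power with 98 evaluable patients at 42% versus 21% is about 70% at one-sided 5% or 59% at one-sided 2.5%, instead of 80%. Restoring 80% would need about 130 evaluable patients (one-sided 5%) or 160 to 170 (one-sided 2.5%), so the sponsor must either accept the lower power or enrol more.

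### The printed rNPV formula has n6 where the protocol's own table requires n7 in the dPCR denominator; applied literally, the ratio could not exceed 1

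*Protocol*

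**What the plan says.** The primary endpoint is the negative predictive value (NPV) of dPCR. The decision statistic is rNPV, the NPV of dPCR divided by that of Q-RT-PCR. Success requires a lower 95% confidence limit above 1.5 (Analyses).

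The Sample size section gives the only algebraic form:

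- dPCR term: "n_{3+} n_4) / (n_{3+} n_4 + n_{6+} n_8"
- Q-RT-PCR term: "n_{2+} n_4) / (n_{2+} n_4 + n_{6+} n_8"

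The relapse part of the denominator, n6+n8, is the same in both.

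The table below the formula classifies patients by dPCR and Q-RT-PCR at entry. Its dPCR-negative row holds n3 and n4 (no relapse within 3 years) and n7 and n8 (relapse), with row totals n3+n4 and n7+n8. The cell n6 is in the dPCR-positive row.

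Two sentences define the statistic in words. Sample size: "where rNPV is the ratio of the Predicted Negative Values by the two tests respectively". Analyses: "rNPV will be calculated as the ratio of the Predicted Negative Values by the two tests respectively".

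For planning, the protocol states that "n₃ and n₇ were assumed to be 0". Study Design and Methods admits patients "with at least 18 months of consecutive negative standard Q-RT-PCR as performed in their own centers".

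**The concern.** An NPV is the share of test-negative patients who stay free of relapse. Its denominator must contain test-negative patients only. The printed dPCR term leaves out n7 and brings in n6, the patients whom dPCR flagged and who did relapse. Correct positives of the test are thus counted against its negative predictive value. The sum n6+n8 is the total of Q-RT-PCR-negative relapsers. It belongs in the Q-RT-PCR term and appears to have been carried into the dPCR term.

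The formula defines the statistic on which the trial is judged, and the protocol assigns the analysis to a named organisation or its designee. A programmer who coded the algebra as written would obtain a statistic that cannot show a benefit of dPCR in this population, however good the assay is.

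**Working it through.** **Inputs, all from the Sample size section.** N = 98. NPV of Q-RT-PCR "equals to the lower limit of the 95% CI of the relapse free rate reported above i.e. 28" per cent. dPCR-negative share: "only 1/3 of patients negative by Q-RT-PCR are also negative by dPCR". Planned ratio 1.5. n3 = n7 = 0.

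**Step 1: the term that the table requires.**

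- NPV of dPCR = (n3+n4)/(n3+n4+n7+n8)
- NPV of Q-RT-PCR = (n2+n4)/(n2+n4+n6+n8), as printed

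**Step 2: the stated sample size.** Planned NPV of dPCR: d = 1.5 × 0.28 = 0.42. With p = 0.28, f = 1/3 and the correct dPCR term, the paired delta-method variance of log rNPV (per patient) is

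V = (1−d)/(f·d) + (1−p)/p − 2(1−d)/p = 4.143 + 2.571 − 4.143 = 2.571.

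At one-sided alpha 0.05, 80% power and a null ratio of 1, n = (1.645 + 0.842)² × 2.571 / (ln 1.5)² = 96.7, so 97 against the stated 98. The delta method, the one-sided test and the null ratio of 1 are assumptions of this check. The protocol cites a reference for its method, does not state sidedness, and writes the null as 1.5. A two-sided alpha gives 123.

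**Step 3: expected cells at N = 98.**

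- n4 = 98 × (1/3) × 0.42 = 13.72
- n2 = 98 × 0.28 − 13.72 = 13.72
- n8 = 98 × (1/3) × 0.58 = 18.95
- n6 = 98 × 0.72 − 18.95 = 51.61

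**Step 4: the two versions at these values.**

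| | NPV of dPCR | NPV of Q-RT-PCR | rNPV |
|---|---|---|---|
| As printed (n6+n8) | 13.72/84.28 = 16.3% | 28% | 0.58 |
| Per table (n7+n8) | 13.72/32.67 = 42% | 28% | 1.50 |

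Only the second recovers the planned 1.5.

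**Step 5: the upper bound.** Put n3 = n7 = 0 and R = n6+n8. The printed ratio is [n4/(n4+R)] / [(n2+n4)/(n2+n4+R)]. Since x/(x+R) rises with x and n4 ≤ n2+n4, the ratio is at most 1, with equality only if n2 = 0 or R = 0. An exhaustive search over all tables with N = 98 and n3 = n7 = 0 gives a maximum of exactly 1.0. If the estimate is at most 1, its lower confidence limit cannot exceed 1.5.

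**Step 6: what the printed ratio fails to see.** It depends on n6 and n8 only through their sum, so moving relapsers from correctly flagged to falsely reassured leaves it unchanged. A perfect test (n2 = n8 = 0) scores 1.00, and so does a test that calls everyone negative (n2 = n6 = 0). With the correct term and a Q-RT-PCR value of 28%, these score 1/0.28 = 3.57 and 1.00.

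**The case against.** The strongest reply is that this is one wrong subscript in a document that otherwise defines the statistic properly. The two verbal definitions, the labelled ratio and the table margin all point to n7+n8, and the Analyses section states the success rule next to the verbal definition without referring to the printed algebra. A competent analyst would compute a true NPV. This stands, and it makes the harm conditional on literal use of the formula.

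A reader might infer that the trial cannot meet its success rule because of this formula. The documents do not support that. They do not show that the printed algebra is what will be programmed, and their words say otherwise.

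A reader might also infer that the sample size is wrong for this reason. Again no: 98 is reproduced to within one patient with the correct term, and a planned ratio of 1.5 could not arise from the printed one when n3 = 0.

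Two technical reservations also stand. First, the bound of 1 belongs to this design and not to the formula in general, because it needs n3 ≤ n2. With n2 = 5, n3 = 20, n4 = 10, n6 = 40 and n8 = 10 the printed ratio is 1.63. The entry criteria and the n3 = 0 assumption exclude such a table here. Second, the equation is available only as machine-read text in which plus signs have moved into subscripts, so a misread digit cannot be ruled out.

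What the reply does not remove is the conflict itself: as it reads, the only algebraic definition of the decision statistic disagrees with the table it refers to.

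**Conclusion.** The point holds in conditional form. The printed NPV of dPCR uses n6+n8, while the table and the verbal definitions require n7+n8. Used literally in this Q-RT-PCR-negative population, rNPV could not exceed 1, would be 0.58 instead of 1.50 at the planning values, and could never satisfy the success rule. The size rests on the protocol's planning figures (28%, one third, 1.5, N = 98). The bound rests on n3 = n7 = 0, which is assumed for planning and follows from eligibility.

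The likely explanation is a transcription slip that did not enter the sample size. It still needs correcting before analysis, because it concerns the primary decision statistic.

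It would be wrong to conclude that correcting the index makes the success rule attainable with 80% power. The null margin and the assumed alternative are both 1.5. With the correct formula and a true ratio of 1.5, simulation at N = 98 gives a lower limit above 1.5 in about 3% of trials (two-sided 95%) to 6% (one-sided 95%). That is a separate problem.

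**What to change.** 1. Check the subscript in the original PDF.
2. If it reads n6, change the denominator of the dPCR term to n3+n4+n7+n8. Leave the Q-RT-PCR term, (n2+n4)/(n2+n4+n6+n8), unchanged.
3. Confirm that the analysis program takes dPCR-negative relapsers as n7+n8. The expected cells at N = 98 make a quick test: the program should return 42% and 1.50.

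The cost is one index in the protocol and a code check. No patients, data or redesign are needed. The coincidence of null margin and alternative at 1.5 has to be dealt with separately.

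### 98 patients do not give the stated 80% power: under the printed rule power is about 3 to 6%, and with the null and threshold set to 1 it is still only just under 70% at the planning values

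*Protocol*

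**What the plan says.** The protocol's Sample size section sets the target: "Sample size will be calculated so to provide with 80% power the alternative hypothesis" that the NPV of dPCR exceeds that of Q-RT-PCR by a ratio of more than 1.5. The hypothesis is one-directional, "H_1(N): rNPV > \delta".

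The inputs follow in the same section:
- The NPV of Q-RT-PCR "equals to the lower limit of the 95% CI of the relapse free rate reported above i.e. 28"%. The protocol adds that a higher true value would give more power.
- From the pilot work, "only 1/3 of patients negative by Q-RT-PCR are also negative by dPCR".
- Cells n3 and n7 are taken as zero.
- The error rates and ratios are given as "With $\alpha=0.05$, $\beta=0.20$, $\delta=\gamma=1.5$ under the alternative hypothesis".

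From these, "under the alternative hypothesis and the above assumptions the sample size required calculated according to reference (42) is 98 patients". The Analyses section gives the success rule: "If the lower 95% confidence limit will be greater than 1.5 one would conclude" that dPCR predicts better. The protocol does not say whether alpha or the 95% limit is one- or two-sided, which interval method is meant, or which variance the sample size formula used.

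**The concern.** The printed inputs fix the distribution of the data, so whether 98 patients give 80% power at 5% can be checked from the protocol alone.

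With null and true ratio both 1.5, the hypothesised effect lies on the null boundary and no finite sample size gives 80% power. The obvious repair is to set the null and the threshold to 1 and leave 98 and 80% as they are. That repair would print another power figure that does not hold. If the limit were then computed by the method that appears to lie behind 98, it would also print an alpha that does not hold.

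The Study Rationale says that a positive result would support a policy of stopping or continuing imatinib on dPCR status. Both the chance of missing a useful test and the chance of endorsing a useless one therefore matter.

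**Working it through.** **Inputs (Sample size section).** N = 98; NPV of Q-RT-PCR P = 0.28; true ratio 1.5; dPCR-negative share w = 1/3; n3 = n7 = 0; alpha 0.05; beta 0.20. NPV is taken in its usual sense, the relapse-free share among test negatives.

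**Implied rates.** In dPCR negatives p1 = 1.5 × 0.28 = 0.42. In dPCR positives (0.28 − 0.42/3)/(2/3) = 0.14/0.667 = 0.21. The expected split is about 33 dPCR negative and 65 dPCR positive. All patients are Q-RT-PCR negative at entry, so P is the weighted mean of the two rates. A ratio above 1 is then the same hypothesis as a higher relapse-free rate in dPCR negatives than in dPCR positives.

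**Reproducing 98.** The large-sample variance of log(rNPV) is V/N with

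V = (1 − p1)/(p1·w) + (1 − P)/P − 2(1 − p1)/P.

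- Under the alternative (p1 = 0.42): V = 4.143 + 2.571 − 4.143 = 2.571.
- At a ratio of 1 (p1 = 0.28): V = 7.714 + 2.571 − 5.143 = 5.143, twice as large.

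With null ratio 1, one-sided 0.05 and the variance under the alternative:

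N = 2.571 × (1.645 + 0.842)² / (ln 1.5)² = 96.7, so 97. Rounded z and log values can give 97.2, hence 98. Nominal power at 98 is 80.5%.

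Other variants miss 98: two-sided 0.05 gives 123; the null variance in the alpha term gives 157; a null of 1.5 divides by ln 1 = 0. The printed 98 is therefore consistent with the first variant. This is an inference, because reference (42) is not at hand.

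**Exact power at 98.** The number of dPCR negatives follows Bin(98, 1/3), and the relapse-free counts are binomial within each group: 0.42 and 0.21 for power, 0.28 in both for the false-positive rate. All outcomes were enumerated. A simulation of 400,000 trials agreed for the one-sided Wald test.

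*Rule as printed (limit above 1.5), Wald limit:* power at a true ratio of 1.5 is 5.9% (one-sided limit) or 3.2% (two-sided).

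*Null and threshold set to 1:*

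| Method | Power | False-positive rate |
|---|---|---|
| Wald log(rNPV), one-sided 5% | 75.3% | 7.4% |
| Score, one-sided 5% | 69.9% | 5.3% |
| Likelihood ratio, one-sided 5% | 68.8% | 5.0% |
| Wald or score, cut-off raised to hold 5% at NPV 28% | 68.7% | at most 5% |
| Mid-p, one-sided 5% | 67.6% | 4.7% |
| Wald, two-sided 95% limit | 66.6% | 4.4% (nominal 2.5%) |
| Score, two-sided 95% limit | 59.1% | 2.8% (nominal 2.5%) |

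No row reaches 80%. The Wald excess arises because the estimated standard error shrinks when the observed ratio is high, as the two values of V show.

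**Sensitivity to the NPV (null 1, ratio 1.5, one-sided).** Score power at 98 is 69.9% at 28%, 73.6% at 30%, 78.8% at 33%, 80.4% at 34% and 87.6% at 39%. The Wald false-positive rate is still 7.0% at 39%.

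**For scale.** Exact 80% power at an NPV of 28% takes about 130 to 135 evaluable patients with the score or mid-p test.

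**The case against.** Much of the case on the other side stands.

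- A null of 1 is not in the protocol, so the 68 to 75% figures describe a design that exists only after another error is corrected. This is true, and the point is framed that way: it says what must not be carried over when that correction is made.
- A reader might infer that the planned analysis has a 7.4% false-positive rate. The protocol does not support that. It names no Wald limit, and a score or likelihood-ratio limit is compatible with its text. Under the printed rule, a Wald limit would exceed 1.5 when the true ratio is 1 in only about 0.02% of trials (one-sided) or 0.01% (two-sided). The 7.4% arises only with a threshold of 1 and a Wald log-ratio limit.
- A reader might infer that 98 is an arithmetic slip, or that the cited method is known to be faulty. Neither can be shown. Under the inferred formula 98 is close to right (97); the fault is that a large-sample formula overstates power with about 33 dPCR negatives.
- The 28% is deliberately conservative, the lower confidence limit of an observed 39%. That margin is real, since score power is about 88% at 39%. But the protocol attaches 80% to 28%, and at that value the figure does not hold.
- Large-sample sizing is normal practice. A discrepancy of a point or two would not deserve comment; one of about ten points does.

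**Conclusion.** The concern holds in this form. The stated combination of 98 patients, alpha 0.05 and 80% power is not delivered at the protocol's own planning values. Under the printed rule power is about 3 to 6%. With the null and threshold at 1, the most favourable repair, it is just under 70% for a one-sided test that holds 5%, and lower with a two-sided 95% limit. A Wald limit would reach 75% only by exceeding its nominal error rate.

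The result assumes a one-third dPCR-negative share, n3 = n7 = 0, a true ratio of 1.5, an NPV of 28%, and all 98 patients evaluable. The last is optimistic: withdrawals and deaths before 36 months are not evaluable, and no inflation of 98 is stated. With an assumed loss of about 5% (93 evaluable), score power is about 68%. The shortfall itself does not depend on how 98 was derived; only the explanation does. It does not mean that the trial is underpowered at every plausible NPV, because score power reaches 80% at about 34%.

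**What to change.** Make this change together with the correction of the 1.5 null and threshold. Restating power while the rule still requires a limit above 1.5 would leave a new contradiction.

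1. In Sample size, set the null ratio to 1 and keep 1.5 as the assumed true ratio. In Analyses, set the threshold for the lower limit to 1.
2. Keep N = 98, delete the 80%, and state exact power as just under 70% at an NPV of 28% with a one-sided 5% test. Add that it is about 80% at 34% and 88% at 39%.
3. State whether the 95% limit is one-sided. If it is two-sided, state the score power of about 59% instead.
4. Specify a score or likelihood-ratio limit for rNPV rather than a Wald limit on the log ratio. At a null of 1, the score version is the score test comparing relapse-free rates in dPCR-negative and dPCR-positive patients.

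The cost is a change of wording and a less favourable stated power. No patients are added.
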